6.2 Secondary Endpoints

Secondary endpoints will include the following:

- The change in HbA1C score during the intervention phase.
- Measure the response rate to text messages in the context of the incentivized reward program
- Responses to the intervention assessment questionnaire.
- Durability analysis of adherence to text message intervention from visit 2 to 3.
- Mean SCI score and HbA1C changes from visit 1 to visit 3 and visit 2 to visit 3.

6.3 Statistical Methods

6.3.1 Baseline Data

Baseline and demographic characteristics will be summarized by standard descriptive summaries (e.g. means and standard deviations for continuous variables such as age and percentages for categorical variables such as gender).

6.3.2 Efficacy Analysis

The primary analysis will include all subjects randomized at Visit 1 who have gotten HbA1c measurements at visit 2. The primary efficacy endpoint will be the change in SCI Score.

The first analysis will be change in SCI score from visit 1 to visit 2 comparing treatment and control groups. For this analysis we will use paired t-tests to test the null hypothesis of no difference in change in SCI scores at the two-sided $\alpha = 0.05$ level.

The secondary analysis will be the change in HbA1c between the intervention and control group from visit 1 to visit 2. For this analysis we will use two sample t-test to test the null hypothesis of no difference in the change in HbA1c at the two-sided $\alpha = 0.05$ level.

An additional secondary analysis will be the durability of the text messaging intervention from visit 2 to 3. SCI score and HbA1C will continue to be tracked to compare visit 1 to visit 3 and visit 2 to visit 3 at study conclusions.

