The main outcome measure will be change HbA1c. The secondary outcome measure will be change in scores of the Self-Care Inventory questionnaire.

PROTOCOL SYNOPSIS

[figure not shown]
Study Title	MyDiaText: Texting the Way to Better Diabetes Control
Funder	NIH T32 Grant-Pediatric Endocrinology Division of CHOP
Clinical Phase	intervention
Study Rationale	Optimal control of type 1 diabetes may prevent, or at least decrease the risk of, diabetes complications. Adolescents with diabetes often have difficulty adhering to a diabetes management plan such a monitoring of blood glucose levels, administering insulin, and eating healthy. There is a need for an intervention that will resonate with youth and support adolescents with type 1 diabetes to improve their self-management practices in order to improve their glycemic control and prevent or reduce the risk of short- and long-term complications.
Study Objective(s)	
Primary
 
 To develop a text messaging intervention using MyDiaText and to determine whether such an intervention will decrease HbA1c in children 12 to 18 years 
Secondary
 
 To determine if a text messaging intervention using MyDiaText will improve diabetes self-management skills as measured by the Self-Care Inventory (SCI) in children 12 to 18 years
Test Article(s)	The intervention will consist of daily text messages sent to the subject's personal mobile device. Previously developed text messages and quiz questions based on the ADA behavior goals will be used for this intervention.
Study Design	Randomized trial
Subject Population key criteria for Inclusion and Exclusion:	
Inclusion Criteria
 
 Subjects age 12 to 18 year of age. Have a diagnosis of T1DM for more than 1 year. HbA1c \geq 8% but $<$ 14%. Have been seen in the diabetes clinic in the last 6 months. Own a personal mobile device with unlimited text messaging plan. Parental/guardian permission (informed consent) and, if appropriate, child assent. 
Exclusion Criteria
 
 Non-English speaking. Significant cognitive disability or major organ illness. Hemolytic anemia.

4. Ongoing oral steroid use	
Number Of Subjects	200 subjects will be recruited from Diabetes Clinics affiliated with the Children’s Hospital of Philadelphia
Study Duration	Each subject’s participation will last for approximately 180 days

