Study Phases	(1) Pre-screening : focus groups to determine details of the intervention
Screening	(2) Screening : screening for eligibility and obtaining consent, review medical record for HbA1C, obtain baseline Self-Care Inventory score
Study Treatment	(3) Intervention : review medical record for HbA1C, obtain Self-Care Inventory score
Follow-Up	(4) Follow-up : review medical record for HbA1C, obtain Self-Care Inventory score, complete satisfaction survey
Efficacy Evaluations	The primary efficacy endpoint will have two parts: the change in HbA1c between control and intervention groups between visit 1, 2 and 3.
Safety Evaluations	Adverse events are not anticipated in this study.
Statistical And Analytic Plan	Descriptive data analysis will include estimating means and standard deviations for continuous variables and counts and proportions of categorical variables for all aims. Two sample t-tests will be used to evaluate changes in HbA1c and SCI scores between the control and intervention groups and paired t-tests (or nonparametric methods if data is not normally distributed) will be used to compares the above changes within each group.
Data and Safety Monitoring Plan	The PI will monitor study progress, ensure the accuracy and security of the data, and ensure subject safety.

TABLE 1: SCHEDULE OF STUDY PROCEDURES

Study Phase	Screening	Control	Intervention	Follow-Up
Visit Number		1	2	3
Study Days		90 (+/- 30 days)	90 (+/- 30 days)	1
Informed Consent/Assent	X			
Review Inclusion/Exclusion Criteria	X			
Randomization	X			
Intake Questionnaire		X		
Height and Weight		X	X	X
HbA1c		X	X	X
SCI Questionnaire		X	X	X
Exit Questionnaire (Subjective Assessment of Intervention)				X

FIGURE 1: STUDY DIAGRAM

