2.1 Primary Objective (or Aim)

The primary objective of this study is to develop a text messaging intervention using MyDiaText and to determine whether such an intervention will decrease HbA1c in children 12 to 18 years. This will be divided into 2 parts:

- To determine whether this intervention will decrease HbA1c in children 12 to 18 years after 3 months +/- 1 month.
- To determine whether the effect of the intervention persists after an additional 3 months +/- 1 month of intervention.

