This phase will start at their next visit with their diabetes provider, which usually occurs after 3 months +/- 1 month. During this phase, control group will continue to not receive text messages, and intervention group will continue to receive text messages. HbA1c and diabetes treatment plan will be collected from the medical record. SCI will be completed at this time. All subjects will get \$10 for completing the second SCI. Invitation to fill out second SCI will be administered via text message. If second SCI is not filled out 7 days after this invitation, a reminder text message will be sent. If not filled out 7 days after reminder text message, a second reminder text message will be sent. No further reminders for that SCI will be sent.

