6 STATISTICAL CONSIDERATIONS

6.1 Primary Endpoint

The primary endpoint will be the change in SCI score between Visit 1 and Visit 2 in control group as compared to intervention group

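### The primary SCI analysis is restricted to subjects with a Visit 2 HbA1c, and the plan does not say how SCI from subjects who stop or are discontinued early enters the Visit 2 comparison

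*Combined protocol and SAP*

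**What the plan says.** Section 6.1 sets the endpoint: "The primary endpoint will be the change in SCI score between Visit 1 and Visit 2 in control group as compared to intervention group". Section 6.3.2 agrees ("The primary efficacy endpoint will be the change in SCI Score") but defines the set by a different variable: "The primary analysis will include all subjects randomized at Visit 1 who have gotten HbA1c measurements at visit 2". It sets no SCI condition.

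Other sections name HbA1c as primary. The abstract says "The main outcome measure will be change HbA1c"; the synopsis, under Efficacy Evaluations, says "The primary efficacy endpoint will have two parts: the change in HbA1c between control and intervention groups between visit 1, 2 and 3"; and section 2.1 has as its first part "To determine whether this intervention will decrease HbA1c in children 12 to 18 years after 3 months +/- 1 month". The sample size in 6.4 is also an HbA1c calculation.

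On collection, section 3.2.3 takes the Visit 2 HbA1c from the medical record (5.3.1 calls it a research lab at each visit) and says of the SCI at that visit, "SCI will be completed at this time". The SCI is invited by text: "If second SCI is not filled out 7 days after this invitation, a reminder text message will be sent". One more reminder follows a week later, then none.

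On leaving the study, section 4.5 lets the investigator discontinue a subject for not adhering to study treatment or to the visit schedule. It also requires that completion be documented for each subject. Section 4.5.1 gives subjects who withdraw the Visit 3 procedures, which include the SCI. It treats a STOP text as withdrawal, followed by a single e-mail. Sections 6.1 to 6.4 contain no missing-data rule, sensitivity analysis or dropout allowance.

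**The concern.** There are two separate issues.

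**The filter.** An analysis set should not depend on a post-randomisation measurement that is not the outcome under analysis. Followed as written, 6.3.2 discards valid SCI change scores because another measurement is absent. The condition fits an HbA1c-primary plan and may be a remnant of one, so the endpoint conflict has to be settled first. If HbA1c is primary, the mismatch goes, but the set still contains completers only.

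**Loss that may depend on arm.** Only the intervention arm receives messages, so only that arm can be discontinued for not adhering to them, and much of the motive for a STOP text lies there. Engagement with the messages is plausibly related to self-care. If subjects leave unequally by arm and those who leave would have had different SCI changes, a comparison of those who remain is biased. Deleting the HbA1c condition does not cure this.

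**Working it through.** **The plan's own figure.** Section 6.4 gives 164 subjects for a 1% HbA1c difference, SD 2.26%, two-sided 0.05, 80% power. For two independent means, n per arm = 2 × (2.26/1)² × (1.960 + 0.842)² ≈ 80.2, so 81. The exact t-based version gives 82 per arm, or 164 in total, with power 80.4%. The figure reproduces as a parallel-group calculation, although the text calls it a cross-over. It supplies no SCI SD and no attrition rate. Recruiting 200 would absorb 18% loss (164/200 = 0.82), but the plan does not state that as an allowance. The inputs below are therefore assumptions.

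**Cost of the filter.** Let a be the share missing SCI, b the share missing HbA1c, and φ the correlation between the two missingness indicators.

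- Both missing: m = ab + φ√[a(1−a)b(1−b)]
- Analysed with the filter: 1 − a − b + m; without it: 1 − a
- Standard-error ratio: √[(1−a)/(1−a−b+m)]
- Usable SCI discarded, of 200: 200(b − m)

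| a | b | φ | m | Analysed | SE increase | SCI discarded of 200 |
|---|---|---|---|---|---|---|
| 0.15 | 0.10 | 0.3 | 0.0471 | 0.797 | 3.3% | 11 |
| 0.15 | 0.10 | 0.5 | 0.0686 | 0.819 | 1.9% | 6 |
| 0.15 | 0.10 | 0.7 | 0.0900 | 0.840 | 0.6% | 2 |
| 0.15 | 0.05 | 0.3 | 0.0308 | 0.831 | 1.2% | 4 |
| 0.15 | 0.05 | 0.5 | 0.0464 | 0.846 | 0.2% | 1 |

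Positive correlation is the relevant case because both measures are tied to the same visit (3.2.3, 4.3.2, 5.3.1). Independence (φ = 0) would give 5.4% at b = 0.10 and 2.6% at b = 0.05.

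**Effect of unequal loss.** Take 100 per arm (200 randomised 1:1), no true effect, and shares q1 (intervention) and q0 (control) lost before Visit 2. In both arms, lost subjects would have changed less favourably than retained ones by a gap g, in SDs of the change score. The retained mean in an arm exceeds the full-arm mean by q × g, so:

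- Bias = (q1 − q0) × g
- SE = √[1/(100(1−q1)) + 1/(100(1−q0))]
- The rejection rate comes from the noncentral t with noncentrality bias/SE, for a two-sample test of change

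| q1 vs q0 | SE | Bias, g = 0.25 / 0.5 | Bias/SE | Two-sided false-positive rate |
|---|---|---|---|---|
| 10% vs 5% | 0.147 | 0.0125 / 0.025 | 0.085 / 0.170 | 5.1% / 5.3% |
| 24% vs 12% | 0.157 | 0.03 / 0.06 | 0.192 / 0.383 | 5.4% / 6.7% |
| 20% vs 5% | 0.152 | 0.0375 / 0.075 | 0.247 / 0.494 | 5.7% / 7.8% |
| 18% vs 18% | 0.156 | 0 / 0 | 0 / 0 | 5.0% / 5.0% |

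Reversing the split reverses the sign of the bias. Deleting the HbA1c condition changes none of these rates.

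**Early-termination SCI.** Section 4.5.1 labels it with Visit 3 procedures, while the primary comparison runs from Visit 1 to Visit 2. Nothing says whether such a value obtained before Visit 2 may stand in at Visit 2. Section 4.5.1 also speaks of subjects who withdraw, and does not clearly cover those whom the investigator discontinues.

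**The case against.** The strongest reply is that the filter is a symptom of the primary-endpoint conflict and costs little. That stands: with both measures taken around one visit, SCI without HbA1c should be uncommon. Even so, the sentence is a wrong rule as long as SCI is primary, and removing it is free.

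A reader might infer more than the documents support:

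- *That SCI is lost after a STOP text or non-adherence.* No section says so. Early-termination procedures include the SCI, the STOP e-mail carries them, and 7.1.1 keeps non-responders eligible for SCI payment. SCI may be lost; what is undefined is its place in the analysis.
- *That handling of missing SCI is left open until unblinded data are seen.* A t-test on change needs both values, so the named analysis is complete-case by default. The narrower gap is that this is unstated and untested.
- *That subjects with HbA1c but no SCI are a harm of the filter.* They lack the outcome under any definition of the set, including the one proposed below.
- *That the trial will be biased.* Discontinuation is discretionary, reminders and SCI payments apply to both arms, prize draws may help retention in the intervention arm, and controls can also withdraw or miss visits. For that last reason, 20% loss against none (6.3-10.2% false positives at the same gaps) is too extreme to lead with.

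**Conclusion.** The point holds in a limited form and should be fixed. What is certain from the text is that 6.3.2 selects subjects for an SCI analysis by HbA1c, that section 6 has no rule or sensitivity analysis for missing SCI, and that the use of early-termination SCI at Visit 2 is undefined.

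The filter probably costs about 0.2-3.3% in standard error, assuming 15% missing SCI, 5-10% missing HbA1c and positive correlation. Unequal, outcome-related loss would put the two-sided false-positive rate at about 5.1-7.8% in the scenarios shown, and at 5% if loss and gap are equal across arms. All loss rates and gaps are assumed. The documents do not establish that unequal loss will occur, or in which direction or by how much it would bias the result. Because completion is documented for each subject, unequal loss could be detected.

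**What to change.** 1. Reconcile the primary endpoint: 6.1 and 6.3.2 against the abstract, synopsis and 2.1.
2. In 6.3.2, delete the Visit 2 HbA1c condition. Analyse all randomised subjects in their assigned arm, each endpoint on its own available data.
3. In 4.5 and 4.5.1, state that stopping messages, or not adhering to them, does not by itself end collection of SCI and HbA1c at Visits 2 and 3, unless the subject withdraws consent or authorisation for data collection. This concerns outcome collection only.
4. In section 6, state that the primary comparison uses complete cases (or name another rule). Add one sensitivity analysis that shifts imputed SCI for lost subjects by 0 to 0.5 SD, by arm. State whether early-termination SCI obtained before Visit 2 may be used at Visit 2.

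Item 2 is a wording change. Items 3 and 4 need a little more follow-up and chart review, one extra analysis, and a check that the combined consent-authorisation document (9.6.2) permits continued collection. The estimated effect may be smaller because non-adherers are counted.

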Interventions using text messages in adolescents with T1DM have been carried out previously with high levels of satisfaction, but variable improvements in diabetes control measured by HbA1c [6,7]. One intervention involved weekly text messages of encouragement based on self-identified barriers to diabetes self-management [8]. This intervention did not result in a change from baseline HbA1c after 3 months of intervention, but a matched historical control group had significant worsening of glycemic control. Another intervention involved automated text or email messages on blood glucose monitoring sent on a self-selected schedule [9]. This intervention showed a slight but not significant improvement in HbA1c after 3 months. Another intervention involved regular text messages based on diabetes goals compared to the same intervention in addition to an intensive insulin regimen [10]. This intervention lasted 12 months and at its conclusion there was a significant improvement in those adolescents receiving the intervention plus intensive insulin regimen, but no significant improvement in those receiving the intervention alone. All of these studies were rather small, with only 18-33 subjects per group. Of these interventions, only the third study reported race/ethnicity information and only included 4% non-White population.

While studies around text messages have been promising, they have not been conclusive. A systematic review of text messaging studies in T1D concluded that while text message interventions are likely a valuable behavioral change tool, that further research should be grounded in behavioral theory[14]. A study in the adolescent T1D population showed that financial incentives for adherence to blood glucose monitoring showed increased monitoring during the incentive period but not in follow up [15]. A study showing the effect of reward for engagement in diabetes education via text message does not exist.

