3.3 Allocation to Treatment Groups and Blinding

Half of the subjects will be randomized to the intervention and the other half will serve as controls. MyDiaText will randomly assign patients to treatment or control upon registration. Given the nature of the intervention, subjects will not be blinded. All study personnel and diabetes providers will not be blinded to current subject phase during the study, since unblinding should not result in bias in this study and it would be difficult to ensure that subjects do not tell their providers whether or not they are receiving text messages.

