6.4 Sample Size and Power

The average HbA1c in adolescents at the CHOP Endocrinology and Diabetes clinic is 9.11% with a SD of 2.26%. Given this average HbA1c and its SD, a sample size of 164 subjects would be needed to observe a difference of 1% in mean HbA1c between groups at a

0.05 level of significance with 80% power in a cross-over study. We will aim to recruit up to 200 subjects out of over 1400 adolescents with T1DM seen at the CHOP Diabetes clinics for their routine care on a yearly basis.

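### Section 6.3.2 names paired t-tests for the between-arm comparison of SCI change; the arms are independent, so this cannot test the stated null, and the synopsis names a different test

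*Combined protocol and SAP*

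**What the plan says.** Section 6.1 defines the primary endpoint as SCI change from Visit 1 to Visit 2, control against intervention. Section 6.3.2 repeats the contrast: "The first analysis will be change in SCI score from visit 1 to visit 2 comparing treatment and control groups". It then names the test: "For this analysis we will use paired t-tests to test the null hypothesis of no difference in change in SCI scores", at two-sided alpha 0.05. The next paragraph of 6.3.2 uses a two-sample t-test for the same contrast in HbA1c.

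The synopsis (Statistical And Analytic Plan) differs for SCI: "Two sample t-tests will be used to evaluate changes in HbA1c and SCI scores between the control and intervention groups". It reserves paired t-tests, or nonparametric methods, for another purpose; these "will be used to compares the above changes within each group".

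On design, section 3.3 states: "Half of the subjects will be randomized to the intervention and the other half will serve as controls". Section 3.2.3 confirms that nobody switches: "control group will continue to not receive text messages, and intervention group will continue to receive text messages". Section 6.4, however, describes its calculation as one "with 80% power in a cross-over study".

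**The concern.** A paired test needs a natural pair for each observation. Here the only pairs are a subject's own Visit 1 and Visit 2 values. A paired test on them asks whether mean change in that arm is zero, which is not the null that 6.3.2 states. Taken at its word, 6.3.2 yields one result per arm and no test of the difference.

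If within-arm results were then used to judge the intervention, two errors become possible. A change shared by both arms (from trial participation or regression to the mean, for example) could be read as an effect. A real benefit could also be missed if controls worsen while the intervention arm holds steady. Section 1.3 describes the second pattern, for HbA1c, in an earlier text-message study: no change on the intervention, while "a matched historical control group had significant worsening of glycemic control".

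The documents also name two different tests for one comparison. That leaves the choice open until after the data are seen, in a trial where study personnel are not blinded (sections 3.3 and 9.1.2).

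**Working it through.** **1. Which design do the plan's own figures imply?** Inputs from section 6.4: HbA1c SD 2.26%, difference 1%, alpha 0.05, power 80%, stated N = 164.

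- Two independent means, normal approximation: n per arm = 2 × (1.960 + 0.842)² × 2.26² / 1² ≈ 80.2, so 81 per arm and 162 in total.
- The same with the noncentral t: 81.15, so 82 per arm and 164 in total. This reproduces the stated figure exactly.
- Paired or cross-over calculation: 83, 59, 43 or 27 subjects at assumed within-subject correlations of 0, 0.3, 0.5 or 0.7. None matches.

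The arithmetic is therefore that of a parallel trial, as in sections 3.2.3 and 3.3. The cross-over label in 6.4 does not fit it.

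**2. What does each test examine?** Let μ_I and μ_C be the mean SCI changes in the two arms.

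- Null in 6.3.2: μ_I − μ_C = 0.
- Paired t-test in the intervention arm: μ_I = 0.
- Paired t-test in the control arm: μ_C = 0.
- Two-sample t-test on change: μ_I − μ_C = 0.

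Only the last matches.

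**3. What could follow from reading within-arm tests?** The documents give no SCI SD, no expected shared change and no rule for reading within-arm results, so these figures are conditional. Arm sizes are 82 (half of 164, a figure sized for HbA1c) and 100 (half of the 200 in section 3.4.2). Shifts are in SDs of change, are the same in both arms, and there is no true effect. Let p be the probability that one arm's paired test is significant (noncentral t, two-sided 0.05). Three possible readings:

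- A: intervention improves significantly, control not significant. This is p(1 − p) for a positive shift; at shift 0 it is 0.025 × 0.95 = 0.024.
- B: exactly one arm significant, 2p(1 − p).
- C: intervention arm read alone, p.

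| Shared shift | A (82 / 100 per arm) | B (82 / 100) | C (82 / 100) |
|---|---|---|---|
| 0 | 0.024 / 0.024 | 0.095 / 0.095 | 0.050 / 0.050 |
| 0.2 SD | 0.245 / 0.250 | 0.491 / 0.500 | 0.432 / 0.508 |
| 0.4 SD | 0.050 / 0.022 | 0.100 / 0.044 | 0.947 / 0.977 |
| 0.5 SD | 0.006 / 0.001 | 0.012 / 0.003 | 0.994 / 0.999 |

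Reading A peaks at 25% and B at 50%. In simulation (100,000 trials per cell, shifts 0, 0.2 and 0.5 SD) the two-sample test rejects in 4.9 to 5.1%.

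**4. The opposite error.** Assume a flat intervention arm and a 0.4 SD decline in controls, a true difference of 0.4 SD. The intervention arm's paired test shows significant improvement 2.5% of the time. The two-sample noncentrality is 0.4 × √(n/2), which is 2.56 at 82 and 2.83 at 100 per arm, giving power of 72% and 80%.

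**5. Could subjects be paired across arms?** Arbitrary pairing keeps the level near 5%, but the plan defines no pairing. It would require equal arms and halve the degrees of freedom (198 to 99 at 100 per arm). The p-value would also depend on the pairing: in one simulated data set it ran from 0.0008 to 0.025 over 5,000 re-pairings, where the two-sample p was 0.009.

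**The case against.** The strongest reply is that this is a wrong test name, not a missing comparison. The endpoint and null in sections 6.1 and 6.3.2 are plainly between-arm, the synopsis names the right test for SCI, and 6.3.2 applies it to HbA1c. An analyst might well run the two-sample test anyway. It is fair that, read together, the documents do contain a valid between-arm SCI test. But 6.3.2 is the detailed efficacy section, nothing says the synopsis overrides it, and the cross-over wording in 6.4 makes the paired test look deliberate.

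Second, the primary endpoint is itself unsettled. The abstract, synopsis and section 2.1 put HbA1c first; only section 6 puts SCI first. If that is resolved in favour of HbA1c, the error falls on a secondary endpoint. This stands as a limit on its reach, but the named test would still be wrong.

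Third, the error rates rest on assumed shifts and reading rules, and run from under 1% to over 99%. At 0.5 SD, readings A and B fall below the nominal 5%. This also stands: they illustrate what could happen and are not the plan's error rate. The study in section 1.3 is likewise only an illustration, since it concerns HbA1c and historical controls.

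**Conclusion.** The concern holds and must be fixed. The test that 6.3.2 names for the section 6 primary comparison cannot test the null it states, and it contradicts the synopsis. Both points follow from the text alone. The size of the consequence cannot be fixed from the documents. Under the assumptions above, a within-arm reading could give false-claim rates from under 1% to over 99%, depending on the shared shift and the rule, whereas a two-sample test stays at about 5%. The two-sample test planned for HbA1c is valid and is not part of the error.

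**What to change.** In section 6.3.2, replace the paired t-tests with a between-arm test, in line with the synopsis. Suggested wording: *The difference between arms in SCI change from Visit 1 to Visit 2 will be tested with a two-sample t-test at two-sided alpha 0.05 and reported with its 95% confidence interval. Paired t-tests within each arm are descriptive, and no efficacy claim rests on them.* The cross-over wording in 6.4 should be reconciled with the parallel design at the same time.

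This costs one or two sentences in 6.3.2, with no new data, visits or subjects. N = 164 is unchanged, since it already matches two independent arms.

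Optional, for precision only: analyse the Visit 2 value by ANCOVA on arm and the Visit 1 value, for both SCI and HbA1c, and report the adjusted difference with its 95% confidence interval. For HbA1c, a normal distribution with mean 9.11 and SD 2.26, cut to the 8 to 14% entry range, has SD 1.43. Assumed clinic-wide visit-to-visit correlations (before that cut) of 0.8, 0.7 and 0.5 then give variance 4%, 7% and 12% lower than raw change, or about 2 to 6% in standard error. No SCI figure can be given. Visit 1 values are already collected.

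### The between-arm tests of change ignore Visit 1 HbA1c and SCI as covariates; baseline-adjusted ANCOVA would gain precision, modestly for HbA1c, at no cost in data

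*Combined protocol and SAP*

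**What the plan says.** For HbA1c from Visit 1 to Visit 2, Section 6.3.2 states: "For this analysis we will use two sample t-test to test the null hypothesis of no difference in the change in HbA1c". For SCI over the same interval, compared between treatment and control, it states: "For this analysis we will use paired t-tests to test the null hypothesis of no difference in change in SCI scores". The synopsis (Statistical and Analytic Plan) differs on SCI: "Two sample t-tests will be used to evaluate changes in HbA1c and SCI scores between the control and intervention groups". It keeps paired t-tests for changes within each group.

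Neither document part mentions ANCOVA, regression, a mixed model or a baseline covariate. Section 6.3.1 uses baseline data for descriptive summaries only. Both baselines are nevertheless planned for everyone: HbA1c at each visit (Sections 4.3 and 5.3.1) and SCI at registration (Section 3.2.2).

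**The concern.** A raw change score subtracts the whole baseline value, which amounts to fixing the slope of follow-up on baseline at 1. With similar spread at both visits and imperfect correlation, the true slope is below 1. Two things follow. The standard error is larger than it need be, and any chance difference between arms at Visit 1 passes in part into the estimated effect. Sections 3.3 and 9.1.1 describe no stratification by baseline HbA1c or SCI that would limit such a difference.

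This matters most for SCI. Section 6.1 makes SCI change the primary endpoint, yet the plan gives it no SD, target difference or power calculation. Precision there is worth having because the power is unknown.

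**Working it through.** **Inputs.** Section 6.4 gives mean HbA1c 9.11%, SD 2.26%, a target difference of 1 percentage point, 5% significance, 80% power and 164 subjects. Section 6.3.2 makes the tests two-sided. Section 3.5.1 restricts entry to HbA1c from 8% to below 14%. Section 3.3 gives 1:1 allocation. No baseline-to-follow-up correlation r is stated; Section 6.4 works from "Given this average HbA1c and its SD". The values of r below are assumptions.

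**Step 1: the plan's own figure.** The normal approximation gives n per arm = 2 × (1.960 + 0.842)² × 2.26² / 1² = 80.2, so 81 per arm and 162 in total. The t-based calculation gives 81.15, rounded up to 82 per arm, which is 164. The stated figure is therefore a parallel, unadjusted comparison of two HbA1c means, although Section 6.4 says "0.05 level of significance with 80% power in a cross-over study". It uses no baseline information. With equal variances at both visits, the variance of change is 2(1-r) × 2.26², which equals 2.26² only at r = 0.5. So 164 does not settle the power of the planned test.

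**Step 2: general formula.** Let β be the slope of follow-up on baseline, Vx the baseline variance and Ve the residual variance. Per subject:

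- change score: Ve + (1-β)² × Vx
- ANCOVA: Ve (about one degree of freedom is spent on the covariate)

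The two are equal only at β = 1.

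**Step 3: SCI.** Assume equal variances at both visits, so β = r. The change-score variance is 2(1-r)σ² and the ANCOVA variance is (1-r²)σ². The ratio is (1+r)/2 and the saving is (1-r)/2: 35% at r = 0.3, 25% at 0.5, 15% at 0.7 and 5% at 0.9. Without an SCI SD or target difference, this cannot be turned into power.

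**Step 4: HbA1c.** Assume clinic HbA1c is normal (9.11, 2.26) with the same SD at both visits and clinic-wide correlation r. Truncating baseline to 8 to <14% gives a baseline SD of 1.43, so Vx = 2.039. Selecting on baseline leaves the slope at β = r and leaves Ve = 2.26² × (1-r²). At r = 0.7, Ve = 5.1076 × 0.51 = 2.605 and the change-score variance is 2.605 + 0.09 × 2.039 = 2.788, a ratio of 0.934.

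Power is for a 1-point difference with 82 per arm, from the t distribution, ignoring the one degree of freedom:

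| Clinic-wide r | ANCOVA / change variance | Saving | Power, change score | Power, ANCOVA |
|---|---|---|---|---|
| 0.3 | 0.823 | 18% | 76.4% | 84.0% |
| 0.5 | 0.883 | 12% | 86.3% | 90.2% |
| 0.6 | 0.909 | 9% | 91.9% | 94.1% |
| 0.7 | 0.934 | 7% | 96.8% | 97.6% |
| 0.8 | 0.958 | 4% | 99.6% | 99.7% |
| 0.9 | 0.979 | 2% | >99.9% | >99.9% |

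**Step 5: chance imbalance.** Under the same model, the standard error of the baseline difference at 82 per arm is 1.43 × √(2/82) = 0.223. An imbalance of two standard errors is about 0.45 points. It shifts the change-score estimate by (1-r) × 0.45: about 0.13 points at r = 0.7 and 0.22 at r = 0.5, against a design difference of 1 point. ANCOVA removes this shift.

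**The case against.** The strongest reply is that nothing here is an error. In a 1:1 randomized trial the two-sample t-test on change is unbiased over randomization and holds its type I error. The imbalance in Step 5 is conditional on the sample drawn. For HbA1c, which Section 6 treats as a secondary analysis, the power gain at 82 per arm is about 2 points or less for r of 0.6 and above, and a target of 200 subjects shrinks it further if retention is good. All of this stands. It limits the point to an improvement in precision; it does not remove the case for one that needs no new data.

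A reader might also infer that the 8% entry criterion pushes the slope below 1 and so makes matters worse. It does not. Under a linear relation, selection on baseline leaves the slope unchanged. It cuts the baseline SD from 2.26 to about 1.43, which makes the gain smaller.

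Another possible reply is that baseline SCI may be incomplete, since it is answered through a text link. The change score needs the same value, so ANCOVA loses no further subjects.

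**Conclusion.** The point holds as a free improvement. The planned tests of change are unadjusted although the baseline is scheduled for everyone. For HbA1c the variance saving is about 2-9% for assumed clinic-wide r of 0.9 to 0.6, rising to about 12% at 0.5 and 18% at 0.3. This rests on a normal clinic distribution with equal SDs at both visits, truncated at entry. For SCI the saving is (1-r)/2 if variances are equal at both visits. The documents supply no correlation for either outcome.

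A reader might apply (1+r)/2 to HbA1c and conclude that power would rise from 80% to about 90%, 86% or 82% at r = 0.5, 0.7 or 0.9. The documents do not support that. The formula needs equal variances at both visits, which the entry restriction breaks under the model in Step 4. Nor is 80% what the protocol's inputs give for the change-score test across that range.

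The paired t-test named for SCI in Section 6.3.2 is a different and more serious matter. It cannot compare two independent arms and it contradicts the synopsis. It must be corrected whether or not adjustment is adopted.

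**What to change.** In Section 6.3.2 and the synopsis, pre-specify before results are seen:

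- a linear model of Visit 2 SCI, and separately of Visit 2 HbA1c, on arm plus the Visit 1 value of the same outcome;
- the adjusted difference between arms with its 95% confidence interval, tested at two-sided 0.05;
- the same model for the Visit 3 values;
- the two-sample t-test on change as a sensitivity analysis.

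The SCI model replaces the paired t-tests now named for that between-arm comparison, so one edit also resolves the conflict with the synopsis. Because Section 3.2.2 places both randomization and the baseline SCI at registration in an unblinded trial, state that SCI is completed before the subject learns the assigned arm. The change score has the same dependence.

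The cost is wording in the analysis plan. No new data, visits or subjects are needed.
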